2.1 Study Rationale

Perception Neuroscience is developing PCN-101 (R-ketamine) for at-home treatment of TRD. Evidence from nonclinical depression model studies suggests that R-ketamine may have equal or potentially greater efficacy compared with S-ketamine, and both nonclinical and clinical studies suggest that R-ketamine may have a more favorable safety profile with a decreased incidence of adverse events (AEs) (eg, dissociative, cognitive impairment, and psychotomimetic effects) compared with S-ketamine. Based on nonclinical studies, R-ketamine may also have less abuse potential than S-ketamine. Overall, the available data support the concept of the use of PCN-101 as a potentially better tolerated, rapidly acting antidepressant compared with ketamine and S-ketamine. Protocol PCN-101-21 is a proof-of-concept study to assess efficacy and safety to provide evidence that PCN-101 can be developed as a rapidly acting antidepressant for the potential treatment of TRD.

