8.2.6 Modified Observer's Assessment of Alertness/Sedation

The MOAA/S will be used to determine if PCN-101 causes the side effect of sedation and to what degree. Sedation will be evaluated by the study staff using the MOAA/S. The observer will record the subject's alertness predose, every 20 minutes for first 2 hours postdose, and at 4 and 6 hours after the start of the infusion.

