For the C-SSRS: suicidal ideation and behavior scores at each assessment time as well as the incidence rate of TEAEs will be summarized using frequency counts and percentages by treatment group.

For the CADSS, BPRS+, 5D-ASC, and MOAA/S: Descriptive statistics of scores and their changes from baseline will be summarized at each assessment time by treatment group.

Pregnancy test and urine drug and alcohol screen will be presented in by-subject listings.

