* An abbreviated version (ie, QIDS-SDR-14) is only done once at Visit 2 'discharge' timepoint. For this timepoint, the decreased/increased weight items score from Day 1 predose will be carried forward to Visit 2 in the calculation of the total score at Visit 2 'discharge'.

III. Study Design

A. Design Overview

This is a Phase 2a, double-blind, randomized, placebo-controlled, multicenter study comprised of 3 phases: screening (up to 2 weeks), [Day -15 to Day -2], In-Clinic

Treatment (Day -1 to Day 2; including double-blind treatment [Day 1]), and post-treatment follow-up (7 and 14 days after infusion, on Days 8 and 15, respectively). The study consists of 3 arms: placebo, PCN-101 Solution for Injection 30 mg, and PCN-101 Solution for Injection 60 mg. A total of 93 adult subjects with TRD will be randomly allocated in equal cohorts of 31 subjects/arm to the 3 arms of the study in a blinded manner. Randomization will be stratified by region (US, EU).

Subjects will be randomized within 14 days of screening (Visit 1). Subjects will be admitted to the clinic the evening prior to study treatment administration (Day -1, Visit 2) and undergo baseline testing to ensure continued study eligibility. Study treatments will be infused IV over 40 minutes the next morning (Day 1, Visit 2). Starting immediately prior to dosing, subjects will be monitored closely for safety. Additionally, the subjects' alertness, mood, and other psychological parameters will be assessed by clinician- and patient completed scales and questionnaires. Subjects will be discharged no earlier than 24 hours postinfusion and after the final in clinic assessments have been completed (Day 2, Visit 2). Subjects will be asked to return to the clinic approximately 6 days (Day 8, Visit 3) and 13 days (Day 15, Visit 4) after discharge to assess the safety and tolerability of the study treatments and to determine the durability of the antidepressant effect.

During the coronavirus disease 2019 (COVID-19) pandemic, the specific guidance from local public health and other competent authorities regarding the protection of individuals' welfare must be applied. If subjects cannot attend follow up visits in person because of restrictions arising as a consequence of the COVID-19 pandemic, the Investigator must discuss with the Medical Monitor potential mitigation.

B. Study Population

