Eligibility for participation in the study will be based on the inclusion/exclusion criteria. Specifically, candidates must meet all entry criteria at Screening or at the time point specified in the individual eligibility criteria listed in the protocol.

Prospective approval of protocol deviations to recruitment and enrollment criteria, also known as protocol waivers or exemptions, is not permitted.

C. Sample Size Predictions

The intent of the primary efficacy analysis is to demonstrate superiority of at least 1 therapeutic dose of PCN-101 Solution for Injection (30 mg or 60 mg) versus placebo based on the change in the MADRS total score from predose to 24 hours postdose.

For the primary analysis, a sample size of 93 randomized subjects (31:31:31) will provide 80% power to detect an 8-point difference between each PCN-101 Solution for Injection dose and placebo in the mean change from baseline MADRS total score at 24 hours postdose, using a t-test with $\alpha = 0.05$ (2 tailed) and assuming a common standard deviation (SD) of 11.

Approximately 20 study centers in the EU and US are expected to participate in this study. The enrollment of 93 subjects is planned. Subjects who do not receive a dose of study treatment on Day 1 (Visit 2) will be replaced.

D. Treatment Randomization

Two doses (30 mg and 60 mg) of IV PCN-101 will be compared with placebo to determine the most effective dose in improving depressive symptoms in subjects with TRD.

Randomization will be used to minimize the bias in the assignment of subjects to treatment arms and to increase the likelihood that known and unknown subject characteristics are evenly balanced across treatment arms. Randomization will be stratified by region (US, EU). This will improve the validity of the statistical comparisons among treatment arms across different geographical regions. Blinded treatment will be used to reduce any potential bias during the collection of data and the analysis of clinical endpoints.

E. Assessment Schedule

The various assessments that will be conducted during this study are summarized in the protocol.

IV. Interventions

A. Clinical Trial Material

The investigational medical products are PCN-101 (30 mg and 60 mg) and Placebo.

V. General Analytical Considerations

A. Data Sources

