Subjects are counted only once in each therapeutic class category. Prior and concomitant medications will be summarized separately and tabulated for each treatment group using frequencies and percentages. Percentages will be based on the number of subjects in each treatment group. Prior and concomitant medications and therapies will be listed by subject.

I. Assessments of Alertness/Sedations and other Safety Rating Scales

For the following rating scales, summaries of actual values (total scores) and changes from baseline will be presented by treatment group for each scheduled assessment timepoint, beginning with the Baseline visit.

A listing displaying the scores for these scales (individual items and total) will be provided by subject.

- Modified Observer's Assessment of Alertness/Sedation (MOAA/S)
- Clinician-Administered Dissociative States Scale (CADSS)
- Brief Psychiatric Rating Scale - Modified 4 Components (BPRS+)

The 5-Dimensional Altered States of Consciousness Rating Scale (5D-ASC) is only assessed post-baseline and for only one (1) time during the study. A listing displaying the details of the 5D-ASC will be provided by subject.

J. Others

Any other assessments which were not described in any previous sections will be listed based on the FAS. This includes (and not limited to) the following:

- Non-compliance in inclusion or exclusion criteria
- Massachusetts General Hospital Antidepressant Response Questionnaire (MGH-ATRQ)
- Mini-International Neuropsychiatric Interview (MINI)

IX. Interim Analysis

No interim analysis is planned.

X. References

XI. Appendices

A. Missing or Partial Date Imputation

For records with missing AE onset/resolution date, the following procedure will be employed for use in determining whether the AE is treatment emergent:

- AE onset dates with missing day and non-missing month will be assumed to occur on the first day of the non-missing month, except for AEs occurring in the month and year of first dosing, in which case the date will be imputed using the date of first dosing.

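### MOAA/S, CADSS and BPRS+ are tabulated only by timepoint, so no scale-based table shows each subject's worst post-dose score by arm

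*SAP*

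**What the plan says.** SAP VIII.I covers MOAA/S, CADSS and BPRS+ together: "summaries of actual values (total scores) and changes from baseline will be presented by treatment group for each scheduled assessment timepoint". Subject-level data appear only as a listing: "A listing displaying the scores for these scales (individual items and total) will be provided by subject". Protocol 9.4.3 agrees: "Descriptive statistics of scores and their changes from baseline will be summarized at each assessment time by treatment group". Under SAP V.I, a summary of continuous data means n, mean, SD, minimum, quartiles, median and maximum.

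The protocol states what MOAA/S is for: "The MOAA/S will be used to determine if PCN-101 causes the side effect of sedation and to what degree" (section 8.2.6). It is taken at eight post-dose checks: every 20 minutes to 2 hours, then at 4 and 6 hours. CADSS and BPRS+ are each taken at three: end of infusion, 2 hours and 4 hours (sections 8.2.7 and 8.2.8).

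Other safety measures get per-subject counts in the SAP:
- Vital signs: incidence of abnormality by treatment against Table 4 (VIII.E).
- QTcF: number and percentage of subjects meeting listed criteria after baseline (VIII.G).
- C-SSRS: subjects answering yes at any post-baseline time (VIII.C).
- TEAEs: subjects by preferred term and by maximum severity (VIII.B).

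**The concern.** Whether the drug sedates, and to what degree, is most directly answered subject by subject: what was the deepest level each person reached, and how does that distribution compare with placebo? A table built one timepoint at a time does not follow a subject across checks. It cannot tell a few subjects affected throughout from many subjects each affected briefly.

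These scales are named safety variables under the secondary safety objective. The protocol introduction links possible use outside a supervised clinic to better tolerability, and notes that dissociative effects are among the reasons S-ketamine is given only in the clinic. The scales nearest to that argument therefore receive a less informative summary than QTcF does. If worst-value tables are added only after unblinding, the choice of summary can be questioned.

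**Working it through.** **The plan's own figures.** The documents give no expected rate, cut-off or precision for these scales, so there is no stated figure to reproduce. The one computed figure in the plan is the 80% power for MADRS. With 31 per arm, difference 8 and SD 11, the noncentrality is 8 / (11 × √(2/31)) = 2.86 on 60 df. Two-sided 5% power is then 80.4%, which agrees. Nothing below depends on it.

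**Inputs.** Arm size 31 (SAP III.A: "randomly allocated in equal cohorts of 31 subjects/arm to the 3 arms of the study"). Post-dose checks: 8 for MOAA/S, 3 each for CADSS and BPRS+. All scores below are assumptions chosen to show a property of the tables; they are not forecasts. I also assume that lower MOAA/S and higher CADSS and BPRS+ mean worse, because the documents do not state the direction.

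**Step 1: can the any-time count be recovered?** Suppose a CADSS total of 20 in 4 of 31 subjects at each of the three checks, and 0 otherwise, including predose. At every check:
- mean = 4 × 20 / 31 = 2.58
- SD = √[(4 × 400 − 31 × 2.58²) / 30] = 6.82
- minimum, Q1, median and Q3 = 0; maximum = 20

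These values are the same in two different situations:
- the same 4 subjects at all three checks: 4/31 = 12.9% affected at any time;
- a different 4 at each check: 12/31 = 38.7%.

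In general, if k subjects are affected at each of T checks, the any-time count lies between k and min(31, kT):

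| Scale | Affected per check | Any-time range |
|---|---|---|
| CADSS or BPRS+ (T = 3) | 4 | 4 to 12 of 31 (12.9% to 38.7%) |
| MOAA/S (T = 8) | 1 | 1 to 8 of 31 (3.2% to 25.8%) |
| MOAA/S (T = 8) | 2 | 2 to 16 of 31 (6.5% to 51.6%) |

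So even a table of counts per level at each check would only bound the any-time figure.

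**Step 2: how much do timepoint means dilute an effect?** Suppose 8 of 31 subjects (25.8%) each fall 2 points on MOAA/S at two checks. The total fall is 8 × 2 × 2 = 32 points.
- Spread evenly over eight checks: 32/8 = 4 points per check, so the mean shift is 4/31 = 0.13. Two of 31 (6.5%) are below baseline at any one check. The quartiles do not move, but the minimum change is −2 and the SD of change is √[(2 × 4 − 31 × 0.129²) / 30] = 0.50.
- All at the same two checks: 16 points per check, so the mean shift is 16/31 = 0.52. Under the SAS default rule Q1 is the 8th ordered value (31 × 0.25 = 7.75, rounded up). That value belongs to an affected subject, so Q1 falls by 2.

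**Step 3: chance inflation of a worst-of-several count.** If each check had an assumed, independent 5% chance of a spurious worsening, the chance of at least one is 1 − 0.95⁸ = 33.7% over eight checks and 1 − 0.95³ = 14.3% over three, in every arm.

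**The case against.** **Affected subjects are counted elsewhere.** A reader might infer that no table in the plan shows how many subjects were sedated or dissociated. That is not so. TEAE tables count subjects by preferred term and by worst severity. Protocol section 8.0 makes AE review continuous from predose to 4 hours. Appendix 4 treats abnormal safety assessments, including worsening from baseline, as AEs when the investigator finds them clinically significant, so scale findings have a route into those tables. This stands, and it limits the point to scale-based tables. The route is still a matter of judgement with no fixed rule linking a score to an AE. Protocol 9.4.3 also leaves TEAEs of special interest to the SAP, which names none.

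**The signal may be visible anyway.** It is tempting to say that the planned tables would look clean while a quarter of an arm was sedated. The documents do not support this. Nothing in them says that subjects peak at different checks. All receive a single infusion planned over 40 minutes, and CADSS and BPRS+ are timed to its end, so aligned peaks are at least as plausible. Step 2 shows that aligned effects move both the mean and Q1. Even dispersed effects show in the minimum and SD. What remains is that these statistics do not say how many subjects were affected.

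**The protocol does not promise an incidence on these scales.** The study rationale says that "R-ketamine may have a more favorable safety profile with a decreased incidence of adverse events", but this is background about AEs relative to S-ketamine, and the trial has no S-ketamine arm. It sets no question for these scales. Likewise, use outside the clinic is only something the data may support; this phase 2a study does not rest on it.

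**The SAP follows the protocol, and the data are listed.** Both are true. Counts could be compiled from listings for 93 subjects, and SAP V.I allows continuous variables to be grouped into categories. That clause is optional and names no variable or cut-off, so it does not prespecify the table.

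**A count of any worsening is noisy.** Step 3 bears this out, so such a count should not be the lead output.

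**Conclusion.** The point holds as a reporting gap, not a data gap. For MOAA/S, CADSS and BPRS+ no scale-based table gives the distribution of worst post-dose scores by arm, and the planned by-timepoint statistics cannot yield it. The size of the ambiguity is shown by the assumed three-check example: 12.9% or 38.7% of an arm affected, with the same table. Whether the timepoint means would also understate an effect is open. In the assumed MOAA/S example the shift is 0.13 points per check if effects are evenly spread and 0.52 if they coincide. The documents give no basis for choosing between these, so dilution is a possibility and not a finding. The improvement is worth making because it is cheap and answers the stated purpose of MOAA/S more directly. It does not affect the efficacy analysis or the validity of the planned safety summaries.

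**What to change.** Before unblinding (the SAP may be modified until database lock), add to SAP VIII.I, for the safety analysis set, by arm and with placebo alongside:

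1. A frequency table of each subject's lowest post-dose MOAA/S level.
2. The distribution of each subject's maximum post-dose change from predose in CADSS total and in BPRS+ total.

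Both are descriptive and need no clinical cut-off. State that the worst value is taken over all available post-dose checks, and whether unscheduled assessments count. If a number and percentage with any worsening from predose is also wanted, label it secondary and read it only against placebo.

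The cost is one derived variable per scale and one table, from data already collected. The drawback is that a worst-of-several value rises by chance in all arms, more for MOAA/S with eight checks than for the scales with three, so the absolute levels should not be quoted without the placebo column.

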8.2.8 Brief Psychiatric Rating Scale - Modified 4 Components

The BPRS+ is one of the oldest, most widely used rating scales to measure psychotic symptoms and will be used by the study staff to measure psychiatric symptoms such as depression, anxiety, hallucinations, and unusual behavior. Only the four-item positive symptom subscale (consisting of: suspiciousness, hallucinations, unusual thought content, and conceptual disorganization) will be used in the study to assess treatment emergent psychotic symptoms. The questionnaire will be administered predose; at 40 minutes postdose (at EoI); and at 2 and 4 hours postdose.

8.2.9 5-Dimensional Altered States of Consciousness Rating Scale

The 5D-ASC will be used to assess the quality of any acute psychological effects of the PCN-101 infusion. It is a retrospectively assessed questionnaire to measure subjective experiences of altered states of consciousness and contains 94 items that are formulated as a visual analog scale. The test will be performed 6 hours after the start of the infusion of PCN-101.

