Table 2 Description of Analysis Sets

Analysis set	Description
Screened Analysis Set	All subjects who signed the informed consent form.
Full Analysis Set (FAS)	
The FAS will consist of all randomized subjects who receive any amount of study treatment and have at least 1 postbaseline assessment available. This population will serve as the basis for efficacy analysis.
 
Subjects will be analyzed according to their randomized treatment.

Safety Analysis Set (SAS)	
The SAS will consist of all randomized subjects who receive any amount of study treatment.
 
This analysis set will be used for all summaries of subject disposition, demographic and baseline data, and safety information including AE incidence.
 
Subjects will be analyzed according to the treatment they actually received.

H. Subgroups of Analysis Populations

Data from subgroups of subjects in the defined analysis populations will be analyzed as specified below. These analyses will comprise descriptive summaries; the goal will be to identify signals of additional effects that analyses of data from the defined populations do not take into account. Such analyses will be considered exploratory and other subgroups may be considered. They may not be sufficient for drawing conclusions; hence, these analyses will not involve hypothesis testing.

- Age Group (18-44, 45-65 years))
- Sex (Male, Female)
- Region (United States or Europe)
- Duration of depression (<5 years, 5-10 years, > 10 years)
- Duration of current episode of depression (weeks)
- Number of previous treatment failures in the current episode (<3, >=3)
- Baseline MADRS Score (<35, ≥35)
- Baseline medication
 - o Selective Serotonin reuptake inhibitor (SSRI)

- o Serotonin and norepinephrine reuptake inhibitor (SNRI)
- o Antidepressant with adjunctive medications

I. Data Display Characteristics

Data displays produced for this study will include three types—summary tables, data listings, and figures. Unless stated otherwise, data listings will be produced for all recorded data. Summary tables will be produced as specified in the following sections. Additional data listings will be produced for outcome measures that involve extensive procedures to derive the analyzed outcomes. Figures will be produced when specified in sections to follow.

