Data listings will simply list the data recorded on the CRF or derived for each subject. They will be ordered by treatment, site, subject number, and time of assessment. When expedient, additional levels of ordering hierarchy may reflect subsets of assessments within subject. Data listings will not display subject initials.

Summary tables will display summary statistics calculated for each of the treatment groups, unless described otherwise in the following sections. Tables may have either of two general layouts. When the greatest interest is in direct comparison of one treatment group with the others at particular times, different columns of a summary table will display the statistics for the different treatment groups.

The summary statistics displayed will be a function of the type of data associated with the summarized assessment. Unless stated otherwise in relevant sections to follow, continuous data will be summarized with the number of non-missing values, arithmetic mean, standard deviation, minimum, quartile 1 (Q1), median, quartile 2 (Q3), and maximum. Categorical data will be summarized with the number of nonmissing values and the numbers of values equal to each of the possible values. Percentages of subjects with each of the possible values will be calculated from the number of subjects in the corresponding analysis population, unless stated otherwise. Some continuous variables may also be grouped into categorical levels and evaluated in frequency tables.

A subset or all of the following tabular column headers will be used in presenting data for the study:

- PCN-101 60 mg
- PCN-101 30 mg
- Placebo

Efficacy analysis will be implemented according to the planned randomization treatment schedule. Safety analysis will be implemented according to the actual dosed treatment.

VI. Subject Accountability

Unless otherwise indicated, the subject characteristics will be presented by treatment groups for the FAS. The same analysis will be repeated for the SAS if the composition of subjects within these analysis sets are different from the FAS.

A. Disposition

Subject disposition events (screened, randomized, completed treatment, completed the study, early discontinuation from the study along with the reason for discontinuation) will be summarized using frequency counts and percentages by treatment groups.

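### The SAP only lists the 5D-ASC by subject, although the protocol states a by-arm descriptive summary of this safety scale

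*SAP*

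**What the plan says.** **Protocol.** Section 9.4.3, under the other safety questionnaires, treats four scales together: "For the CADSS, BPRS+, 5D-ASC, and MOAA/S: Descriptive statistics of scores and their changes from baseline will be summarized at each assessment time", and the sentence goes on to specify treatment group as the unit of summary. The synopsis carries the same sentence. Section 8.2.9 describes the 5D-ASC as a retrospective questionnaire of 94 visual-analog items and fixes its timing: "The test will be performed 6 hours after the start of the infusion of PCN-101". The Schedule of Activities shows no predose administration.

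**SAP.** Table 1 lists the 5D-ASC among the endpoints for the safety objective, which sets two doses of PCN-101 against placebo. Section VIII.I then divides the scales. For the MOAA/S, CADSS and BPRS+, "summaries of actual values (total scores) and changes from baseline will be presented by treatment group for each scheduled assessment timepoint". The 5D-ASC is handled separately: it "is only assessed post-baseline and for only one (1) time during the study", and "A listing displaying the details of the 5D-ASC will be provided by subject". Section V.I limits what else could appear: "Summary tables will be produced as specified in the following sections".

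**The concern.** The two documents disagree on what will be produced for a named safety variable, and the SAP gives the smaller output without saying that it departs from the protocol.

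The scale bears on the programme's argument. Protocol Section 4.3 names the 5D-ASC among the instruments used in the Phase 1 study behind dose selection. It also cites fewer episodes of altered consciousness at 30 mg and 60 mg than at 100 mg and 150 mg. Here the same scale is collected in patients with a concurrent placebo arm, but no statistic by arm is planned.

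There is a second cost. Neither document says how the 94 items become scores. If no score and no table are fixed before unblinding, any later statement about the 5D-ASC by arm would rest on choices made after the data were seen.

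**Working it through.** The plan states no figure on this point, so the check is a comparison of texts.

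1. **What the protocol states.** Four scales are named: CADSS, BPRS+, 5D-ASC and MOAA/S. Each is to have scores and changes from baseline summarised by arm at each assessment time.

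2. **What the SAP plans.**

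| Scale | Assessment times (protocol) | Protocol 9.4.3 | SAP VIII.I |
|---|---|---|---|
| MOAA/S | Predose, every 20 min to 2 h, 4 h, 6 h | By-arm summary | By-arm summary and listing |
| CADSS | Predose, end of infusion, 2 h, 4 h | By-arm summary | By-arm summary and listing |
| BPRS+ | Predose, end of infusion, 2 h, 4 h | By-arm summary | By-arm summary and listing |
| 5D-ASC | 6 h only | By-arm summary | Listing only |

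 Three of the four summaries carry over and one does not.

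3. **Whether another SAP rule restores the table.** It does not. Section V.I makes summary tables depend on a later section asking for them, and no later section asks for one on the 5D-ASC. The default in V.I covers listings. It says of them: "They will be ordered by treatment, site, subject number, and time of assessment". A reader can therefore see which arm each row belongs to, but no arm-level statistic is computed.

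4. **Whether the single assessment explains the omission.** Change from baseline is the post-baseline value minus the baseline value, and SAP V.B sets it to missing when either is missing. With no predose 5D-ASC it is missing for every subject, so that part of the protocol sentence cannot be carried out. The observed 6-hour score needs no baseline. In a randomised trial the placebo arm is the reference, and a mean or median by arm can be calculated from one time point.

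5. **Precision, if a difference were also shown.** With 31 per arm (SAP III.C) and complete data, the 95% CI half-width for a dose-placebo mean difference is t(0.975, 60) × SD × √(2/31) = 2.000 × 0.2540 × SD ≈ 0.51 SD. The documents give no SD for any 5D-ASC score, so this cannot be put in scale points.

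**The case against.** The strongest reply is that the SAP is the detailed document, gives a reason for treating this scale differently, and leaves little uncovered. Several parts of that stand:

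- The protocol sentence cannot be applied in full to a scale given once, so some departure was unavoidable.
- Dissociation, positive psychotic symptoms and sedation are summarised by arm through the CADSS, BPRS+ and MOAA/S, and treatment-emergent adverse events are tabulated by arm.
- No hypothesis test, stopping rule or dose-selection criterion in either document uses the 5D-ASC.
- The tolerability rationale is largely relative to S-ketamine. This trial has no S-ketamine arm, so a dose-versus-placebo table would serve the safety objective and could not test that claim.

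The reply does not cover the observed score. Being assessed once explains the loss of change from baseline and nothing more, and the SAP offers no other reason.

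A reader might go further and infer that altered consciousness cannot be compared between the doses and placebo at all, or that the trial loses its arm-level evidence on psychotomimetic effects. The documents do not support either reading. The data are collected, the listing is ordered by treatment, Protocol 9.4.4 allows exploratory analyses, and SAP I.B allows changes until database lock. The three related scales also remain. Nor do the documents say that the 5D-ASC alone captures the whole acute experience. Section 8.2.9 says only that it assesses the quality of acute psychological effects.

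**Conclusion.** The inconsistency is real and can be read directly from the text: the protocol states a by-arm descriptive summary of the 5D-ASC, and the SAP plans only a by-subject listing. The accurate statement is that no by-arm summary is planned, not that none is possible.

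Its size is one safety endpoint out of four acute-effect scales left without an arm-level result. The number of values in the listing (94 items × 93 subjects = 8,742 if every item is completed) describes the bulk of the output. It is not a bias or an error rate and should not be read as the size of the problem. The primary analysis, its power and its error rate are untouched.

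The conclusion assumes that the protocol in hand is the amended version 4.0 on which the SAP says it is based, and that no separate table shell, outside these documents, already specifies a 5D-ASC table. It is worth correcting because the scale is a named endpoint and the remedy is cheap.

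**What to change.** Before database lock:

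1. In SAP VIII.I, state which 5D-ASC scores are derived (a total, dimension scores, or both), how the 94 items map to them, and whether the missing-item rule in SAP VII.E, which is written for efficacy scales, applies.
2. Add one table of the observed 6-hour scores by treatment group on the Safety Analysis Set, with n, mean, SD, median, quartiles, minimum and maximum. These are the SAP's default statistics for continuous data. Keep the listing.
3. Remove change from baseline for the 5D-ASC from the protocol synopsis and Section 9.4.3. If the protocol will not be amended again, record in the SAP that it is not calculated because there is no predose assessment.

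Dose-placebo differences with 95% CIs are optional. The protocol states only descriptive statistics, the three related scales have no such intervals, and SAP V.F applies no multiplicity adjustment. If shown, they should be labelled descriptive.

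The cost is specifying the score derivation, which has to come first, and programming one table. No new data are needed.
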